9 SAFETY ANALYSES

Unless otherwise specified, all the safety analyses will be based on the safety population by cohort.

9.1 Extent of Exposure

The duration of exposure to study treatment, total number of doses and cumulative dose administered will be summarized for each treatment within each cohort. Relative dose intensity will be additionally calculated for Glembatumumab exposure. The individual dose is calculated using the actual body weight of the patient at baseline, and the dose may remain constant throughout the study unless a greater than 10% change in weight is observed, in which case the weight at the cycle will be used.

The calculations for the above statistics for each treatment in each cohort are as follows:

- Duration of Exposure (days) = Date of Last Dose – Date of First Dose + 1
- Total number of doses= the total number of doses with volume added to bag>0 and total volume infused>0
- The actual dose at each cycle (mg/kg) =
 - **Glembatumumab**: Total Volume infused (mL) / [Volume of Infusion bag (mL)] * Volume of Glembatumumab Vedotin added to bag (mL) * 5 (mg/mL) / weight (kg)
 - **Varlilumab**: Total Volume infused (mL) / [Total volume prepared (mL)] * Volume of Varlilumab added to bag (mL) * 5 (mg/mL) / weight (kg)

- **Nivolumab:** $\text{Total Volume infused (mL)} / [\text{Total volume prepared (mL)}] * \text{Volume of Nivolumab added to bag (mL)} * 10 \text{ (mg/mL)} / \text{weight (kg)}$
- **Pembrolizumab:** $\text{Total Volume infused (mL)} / [\text{Total volume prepared (mL)}] * \text{Volume of Pembrolizumab added to bag (mL)} * 25 \text{ (mg/mL)} / \text{weight (kg)}$
- Cumulative dose for each treatment is the sum of all actual doses for all cycles in mg/kg
- For Glembatumumab, Relative Dose Intensity = Actual Dose Intensity (ADI) / Planned Dose Intensity (PDI), where ADI (mg/kg/3 weeks) = Cumulative Dose (mg/kg) / ((Date of Last Dose – Date of First Dose + 21) / 21) and PDI (mg/kg/3 weeks) = 1.9 mg/kg/3 weeks.

9.2 Adverse Events

Adverse events (AEs) will be coded using the Medical Dictionary for Regulatory Activities Terminology (using latest MedDRA version). All AEs will be presented in a by-subject listing. Safety evaluations will be based on the incidence, severity, type of AEs, clinically significant changes or abnormalities in the subject's physical examination, vision examination, vital signs, ECG, and clinical laboratory results.

These analyses will be performed using the safety population by cohort.

9.2.1 Treatment emergent AE

Treatment emergent AEs (TEAEs) include all AEs that occurred or increased in severity from first dose of study treatment up to 28 calendar days after the last administration of glembatumumab vedotin or 70 calendar days after the last administration of varlilumab (whichever occurs later, Cohort 2); 70 days after last dose of the PD-1 targeted checkpoint inhibitor (whichever occurs later in Cohort 3). In addition, if an AE cannot be determined as treatment-emergent or not due to incomplete/missing data, conservatively, it will be considered as treatment emergent and included in the summary tables. Any AE summary tables described in this plan are based on treatment-emergent AEs unless specified otherwise. The number and percentage of subjects experiencing at least one treatment emergent adverse event will be tabulated by MedDRA primary system organ class, preferred term and cohort. For the number of subjects with AEs, subjects reporting the same event more than once will have that event counted only once within each body system, and once within each preferred term.

A separate summary will be provided for study treatment-related AEs. A study treatment-related AE is defined as an AE for which the investigator classifies the relationship to study treatment as "Related". A worst-case scenario approach will be taken to handle missing relatedness data, i.e., the summary table will include events with the relationship to study treatment as "Related". The number and percentage of subjects experiencing at least one treatment emergent AE considered related to treatment will also be summarized.

TEAEs will also be summarized by NCI-CTCAE version 4.0 grade. Again, multiple occurrences of the same event are counted once per subject using the maximum severity. If the grade of an AE is missing, the event will be included in the total column for the corresponding cohort. TEAEs with actions of study treatment delayed/interrupted, reduced, or discontinued will be summarized in by CTCAE grade. Summary statistics of the number and percentage of subjects experiencing at least one treatment emergent AE by study visit will be presented as well. The subject incidence count for each visit will be from the time of the previous visit, except the baseline visit, where it counts from the time of first dose.

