2. Informed consent may be signed at any time prior to or during the screening period. No study-specific procedures will be performed prior to receipt of signed Informed Consent. However, assessments performed according to standard of care prior to receipt of Informed Consent may be utilized to fulfill the screening requirement, if completed within the required window for screening.
3. Patients will receive study treatment until intolerance, progression of disease, or any of the other criteria for discontinuation of study treatment (Section 7.2.4.1.1) are met. All cohorts will receive glembatumumab vedotin on a three-week cycle. Cohort 2 patients will also receive varlilumab on Day 1 of Cycles 1, 2, 4, 6, 8, and 10. Cohort 3 patients will also receive a PD-1 targeted CPI per institutional standard of care.
4. The End of Treatment Visit should be performed within 28 days after last dose of study treatment and prior to initiation of alternate therapies.

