- Additional clinic visits and monitoring (such as laboratory assessments) relevant to the administration of the PD-1 targeted CPI will be conducted in accordance with standard of care when appropriate. However, all CPI dosing and adverse events occurring between study visits will be documented in the eCRF.
24. All concomitant medication will be documented in the Case Report Form (CRF) if taken within 28 days prior to Study Day 1, and either (whichever occurs sooner): a) 28 days after last dose of study treatment or b) initiation of alternate anti-cancer therapy. In addition, all anti-cancer medications should be recorded throughout the duration of study follow-up.
25. For patients who develop grade 3 treatment-related rash and who provide appropriate consent, punch biopsies and photographs of the rash, as well as uninvolved skin, are strongly encouraged. Samples may be analyzed centrally; in these cases, collection, processing and shipping instructions will be provided separately.
26. Adverse event monitoring on Cycle 1 Day 7 and Cycle 1 Day 14 for patients in Cohorts 2 and 3 can be performed in person or by telephone to determine if the patient is experiencing any adverse events.
27. Events occurring >28 days after discontinuation of glembatumumab vedotin, >70 days after discontinuation of varlilumab (Cohort 2), or >70 days after discontinuation of the PD-1 targeted CPI (Cohort 3) are only reportable if both serious (SAE) and potentially treatment-related.

Table 2. Schedule of Assessments (Cohorts 4 and 5)

Visit	Screening ²	Treatment Visits ³							Disease Assessment Visit ⁵	Survival Assessment ⁶
		Cycle 1/ Day -6 to Day -2	Cycle 1 / Day 1	Cycle 1 / Day 7	Cycle 1 / Day 15-19	Cycle 2 / Day 1	Cycle 3, 4, 5, etc. / Day 1	End of Treatment ⁴		
Visit window¹	Day -35 to Day -7		+3/- 1 days	+/- 1 day		+3/- 1 days	+/- 3 days	Within 28 days post-dosing	Every 6 (±1) weeks for 6 months then every 9 (±2) weeks thereafter	Every 12 (±2) weeks until study closure
Informed Consent, and, if applicable, HIPAA	X									
Tumor tissue ⁷	X ⁸			X ⁸				X ⁹		
Medical history ¹⁰	X	X (Day -6 only)								
Physical examination ¹¹	X	X ¹²	X		X	X	X	X		
Vital signs ¹³	X	X	X		X	X	X	X		
ECOG performance status	X	X ¹²				X	X	X		
Electrocardiogram (ECG)	X							X		
Pregnancy test ¹⁴	X	X ¹²								
Hematology ¹⁵	X	X ¹² (Day -6 only)	X	X	X (Day 15 only)	X	X	X		
Blood chemistry ¹⁵	X	X ¹² (Day -6 only)	X	X	X (Day 15 only)	X	X	X		

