10.2.2.3. AE/SAE Reporting

The investigator is to report all directly observed AEs and all AEs spontaneously reported by the study patient. In addition, each study patient will be questioned about AEs.

AEs and SAEs should be recorded on the CRF from the time the patient has taken at least one dose of study treatment through (whichever occurs first) either: a) 28 calendar days after the last administration of glembatumumab vedotin or 70 calendar days after the last administration of varlilumab (the latter whichever occurs later, Cohort 2); 70 days after last dose of the PD-1 targeted checkpoint inhibitor (the latter whichever occurs later in Cohorts 3 and 5); 28 calendar days after the last administration of CDX-301 (the latter whichever occurs later, Cohorts 4 and 5); or b) initiation of alternate anticancer therapy.

However:

- Any SAE occurring any time after the reporting period must be promptly reported if a causal relationship to study treatment is suspected
- For AEs or SAEs with a causal relationship to the investigational product, follow-up by the investigator is required until the event or its sequelae resolve to \leq Grade 1, or stabilize for at least three months after the last administration of study treatment (whichever is sooner).

All AEs will be reported on the AE page(s) of the CRF, while SAEs will also be reported in an expedited fashion using the SAE Report. The AE CRFs and SAE Reports must be completed in a consistent manner; for example, the same AE term, causality, severity, and onset/resolution dates should be used on both forms.

In case of an SAE (regardless of causality), an SAE Report must be completed and submitted to Celldex within 24 hours of the site's notification of the event, irrespective of the extent of available adverse event information. This timeframe also applies to additional new information (follow-up) on previously forwarded SAE reports. The investigator is obligated to pursue additional information required for thorough evaluation of each SAE as may be requested by Celldex.

Serious adverse event reporting to regulatory authorities and all participating investigators will be conducted by Celldex in accordance with 21CFR312.32 and international regulations, as appropriate.

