11.5.3. Safety Analysis

Safety and tolerability will be assessed by incidence, severity, and changes from baseline of all relevant parameters including AEs, vital signs, and laboratory values.

AEs will be coded using the latest available version of the Medical Dictionary for Regulatory Activities (MedDRA). The number and percentage of patients experiencing one or more AEs will be summarized by relationship to study drug, and severity. Treatment-emergent AEs are defined as AEs that start on or after the first day study drug is administered. AEs will be summarized by the number and percentage of patients who experienced the event, according to system organ class and preferred term. A patient reporting multiple cases of the same AE will be counted once within each system organ class and similarly counted once within each preferred term. Unless specified otherwise, the denominator for these calculations will be based on the number of patients who receive at least one dose of study drug, irrespective of the total number of doses administered. AEs will also be summarized by NCI-CTCAE severity grade and by relationship to study drug. Additional summaries may also be provided for SAEs and events resulting in the permanent discontinuation of therapy. All AEs will be included in individual patient data listings.

Vital sign and laboratory results will be summarized descriptively. The incidence of Grade 3 and 4 hematological toxicities (including neutropenia, thrombocytopenia, and anemia) will be provided. The use of red blood cell and other blood component transfusions and/or growth factor support will be reported. Similar analyses will be done for selected chemistry tests (including liver and renal function tests). Data listings of all vital sign and laboratory data collected during the study will be presented. Laboratory values outside normal limits will be identified in data listings and will include flags for high and low values.

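### Adverse-event percentages by cohort rest on unequal follow-up windows, which can inflate the combination columns; one overview table on a common 28-day cut would remove this

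*SAP*

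**What the plan says.** SAP 9.2.1 opens the window at first dose and closes it "up to 28 calendar days after the last administration of glembatumumab vedotin or 70 calendar days after the last administration of varlilumab", whichever is later in Cohort 2. For the PD-1 inhibitor the limit is "70 days after last dose of the PD-1 targeted checkpoint inhibitor (whichever occurs later in Cohort 3"). Cohort 1 receives glembatumumab vedotin alone, so its limit is 28 days.

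The core table gives the "number and percentage of subjects experiencing at least one treatment emergent adverse event", which "will be tabulated by MedDRA primary system organ class, preferred term and cohort". The related-event and grade tables, and the serious-event table in SAP 9.2.2, are also subject counts and percentages. Protocol 11.5.3 sets the denominator as the "number of patients who receive at least one dose of study drug, irrespective of the total number of doses administered". SAP 9.1 summarises exposure separately, as last dose minus first dose plus one day, so the post-dose window does not enter it. No exposure-adjusted rate, time-to-event analysis of adverse events or cumulative table on a common window is planned. SAP 9.2.1 does plan a summary by study visit.

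Two protocol rules bear on this. Recording under Protocol 10.2.2.3 stops at the end of the window "or b) initiation of alternate anticancer therapy", whichever comes first. Table 1, footnote 27, in the Schedule of Assessments says of "Events occurring >28 days after discontinuation of glembatumumab vedotin, >70 days after discontinuation of varlilumab (Cohort 2"), and of events beyond the corresponding 70-day PD-1 limit, that they are reportable only when both serious and possibly related to treatment.

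**The concern.** The percentage of patients with at least one event can only grow as patients are observed for longer. The cohort columns will sit side by side with different observation times, and nothing in the main tables separates added toxicity from added follow-up. Safety of the monotherapy and of each combination are secondary objectives (SAP 2.1.2), so a reader is likely to look across the columns for what the partner drug adds. Some of an apparent excess could come from the window alone.

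**Working it through.** The documents state no adverse-event rate or safety precision figure, so there is nothing to reproduce. The window lengths come from SAP 9.2.1 and the cycle length is 21 days. The varlilumab schedule is in Table 1, footnote 3: "Cohort 2 patients will also receive varlilumab on Day 1 of Cycles 1, 2, 4, 6, 8, and 10". Treatment time, hazard and its course after treatment are my assumptions.

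**1. Excess window, on-schedule dosing.** Cohort 1 has 28 days after the last glembatumumab vedotin dose.

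- Cohort 3, last doses on the same day: 70 − 28 = 42 days more.
- Cohort 2: window = max(28, 70 − 21k), where k is the number of cycles from the last varlilumab to the last glembatumumab vedotin dose.
  - Last cycle 1, 2, 4, 6, 8 or 10: k = 0, window 70, excess 42.
  - Last cycle 3, 5, 7, 9 or 11: k = 1, window 49, excess 21.
  - Last cycle 12: k = 2, window 70 − 42 = 28, excess 0, and 0 thereafter.

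**2. What changes the excess.** Protocol 8.7 lets a patient stop the partner drug and continue glembatumumab vedotin. If the partner stopped 42 or more days before the last glembatumumab vedotin dose, the excess is zero. The same section lets the PD-1 inhibitor continue after glembatumumab vedotin stops; if those doses count, the excess is more than 42 days. The documents do not say whether they count. Alternate therapy starting by day 28 after the last dose also removes the excess.

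**3. Illustration at equal hazard and equal treatment time.** Let T be days from first to last dose, W the post-dose window, p the Cohort 1 percentage, and f the hazard after day 28 post-dose relative to before. Then λ = −ln(1 − p)/(T + 28), and the combination shows 1 − exp{−λ[T + 28 + f(W − 28)]}. With T = 84 and p = 20%, λ = 0.2231/112 = 0.00199 per day.

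| f | W = 70 | W = 49 |
|---|---|---|
| 1 | 26.4% | 23.3% |
| 0.5 | 23.3% | 21.7% |
| 0.25 | 21.7% | 20.8% |
| 0 | 20.0% | 20.0% |

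T = 84 puts the last on-schedule dose in Cycle 5, so W = 70 applies to Cohort 3 with coinciding last doses and W = 49 to Cohort 2. With f = 1 and W = 70, alternate therapy starting 28, 35, 42 or 56 days after the last dose gives 20.0%, 21.1%, 22.2% or 24.3%. For other treatment times (f = 1, W = 70, Cohort 1 still 20%), the result is 42.8% at T = 0, 30.0% at T = 42 and 23.7% at T = 168.

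**4. Unequal treatment time.** If the combination is given for 42 days and Cohort 1 for 84, total time is 42 + 70 = 112 against 84 + 28 = 112, and both show 20.0%. Still shorter combination treatment would show less than Cohort 1.

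**5. Check of the remedy.** Cutting every cohort at 28 days gives T + 28 throughout, hence 20.0% in each at equal treatment time. Person-time over each cohort's full window works only if the hazard stays constant off treatment. Take two cycles (last dose day 22), full hazard to day 43 and half after that.

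- Cohort 1 to day 50: (43 + 0.5 × 7)/50 = 46.5/50 = 0.93 of the on-treatment rate.
- Cohort 3 to day 92: (43 + 0.5 × 49)/92 = 67.5/92 = 0.734.

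The ratio is 0.734/0.93 = 0.79, so an equally toxic combination would look about 21% safer.

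**The case against.** The best defence is that these tables describe each regimen and compare nothing. The cohorts are non-randomised, differ in eligibility and are analysed separately, and the only cross-cohort comparison named (Protocol 11.5.1) is for efficacy endpoints. The windows match protocol collection and suit the antibodies. The by-visit summary lets a reader compare on-treatment intervals that the post-dose tail does not touch. Events that start early, such as rash in Cycle 1, are little affected because each patient counts once per term.

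Most of this stands. No test is distorted, and a common window would not make the cohorts comparable in other respects. But the by-visit summary mitigates only in part: it is not stated to be split by preferred term, grade, seriousness or relatedness, Cohorts 2 and 3 have additional Day 7 and Day 14 visits, and it gives no cumulative incidence.

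A reader might infer that the combinations will look more toxic than they are. The documents do not support that: the excess may be zero for many patients, and shorter combination treatment can offset or reverse it. Nor do they support calling the 70-day windows an error.

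**Conclusion.** The point holds as a matter of how the tables are presented. At equal hazard and equal treatment time, the longer windows can inflate the combination percentages and never lower them. The size cannot be derived from the documents. With 84 days from first to last dose and 20% in Cohort 1, the combinations would show 20% to 26%. The top of that range needs a full 70-day window and undiminished hazard; the bottom applies if hazard after day 28 is nil or alternate therapy starts by then. A reader might take the larger single-dose figure (42.8%) as typical, but it assumes no treatment beyond the first dose and constant hazard for 70 days, and nothing in the documents supports that as the usual case.

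**What to change.** Keep the current windows for the main tables and listings, and footnote each table with the window used. In SAP 9.2.1 add one overview table for all cohorts (any treatment-emergent event, grade 3 or higher, serious, related), cut at 28 days after the last glembatumumab vedotin dose. That is the longest window in which all events are recorded in every cohort; a common 70-day cut is not possible, because Cohort 1 recording beyond 28 days is limited to serious, possibly related events.

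The common cut removes the window difference but not differences in treatment duration. If exposure-adjusted rates are added for that reason, compute them over the same 28-day window, not over each cohort's full window, where a low-hazard tail would make the combinations look safer. The cost is one extra table set from dates already collected.

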4.1 Safety Population

The safety population will include all patients who receive at least one dose of study treatment of glembatumumab vedotin or varlilumab or a PD-1 targeted CPI. A baseline measurement and at least one laboratory, vital sign, or other safety-related measurement obtained after at least one dose of study treatment may be required for inclusion in the analysis of a specific safety parameter. For each cohort, the safety population constitutes all treated patients and will be used for secondary analyses of ORR and all other endpoints. The safety population is equivalent to the ITT population defined in the protocol.

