5 GENERAL CONSIDERATIONS

Analysis datasets will be created according to Clinical Data Interchange Standards Consortium CDISC/Analysis Data Model (ADaM) standards. SAS v9.4 or higher software will be used to perform all data analyses (ADaM datasets, tables, figures, and listings).

Baseline will be defined as the most recent non-missing value prior to or on the same day of the first dose of glembatumumab vedotin. Generally, only pre-specified planned visits will be used in the by-visit summaries, statistical analyses and calculations of any derived safety parameters except for lab summary tables. All post baseline measurements including scheduled and unscheduled assessments will be used to derive the worst / best assessment for lab summary tables.

The primary response criterion is RECIST 1.1. Confirmation of response is required in defining best overall response (BOR) as the primary endpoint. The irRECIST is used as a secondary analysis for all efficacy endpoints except for OS.

All analyses specified in this plan will be performed by cohort. All baseline tables will include a column for each cohort and a column for overall. Unless otherwise stated, continuous variables will be summarized with n, mean, median, standard deviation, Q1, Q3, minimum and maximum, and categorical variables will be summarized with frequency counts and percentages.

Unless otherwise stated, all listings will be sorted by cohort, subject number, and then by visit date if applicable.

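### The by-visit adverse event table in SAP 9.2.1 mixes interval length and, under the default denominator, attrition with the timing of toxicity (minor)

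*SAP*

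**What the plan says.** SAP 9.2.1 adds one table to the usual TEAE summaries: "Summary statistics of the number and percentage of subjects experiencing at least one treatment emergent AE by study visit will be presented as well". The counting rule is that "The subject incidence count for each visit will be from the time of the previous visit". One row is treated differently from the rest: "except the baseline visit, where it counts from the time of first dose". The section gives no interval length, number at risk or exposure adjustment for this table.

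Three other places bear on the denominator:
- SAP 9.2 says of the adverse event analyses: "These analyses will be performed using the safety population by cohort".
- SAP 4.1 defines that population: "The safety population will include all patients who receive at least one dose of study treatment".
- Protocol 11.5.3 sets a default, which holds where nothing else is laid down: "the denominator for these calculations will be based on the number of patients who receive at least one dose of study drug". The number of doses given does not matter.

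On which visits form the rows, SAP 5 says that generally "only pre-specified planned visits will be used in the by-visit summaries". The schedule (SAP 16.1; Protocol Section 4, Table 1) has dosing visits every three weeks in all three SAP cohorts. It also has "Adverse event monitoring on Cycle 1 Day 7 and Cycle 1 Day 14 for patients in Cohorts 2 and 3" and an End of Treatment visit within 28 days of the last dose.

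**The concern.** A table by visit is there to show when toxicity occurs. Counting from the previous visit makes each percentage depend on how far apart the visits are, and that spacing differs between Cohort 1 and Cohorts 2 and 3 early in treatment. If all treated patients stay in the denominator, each later percentage also depends on how many patients are still on drug.

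With an unchanging event rate, Cohorts 2 and 3 would show low percentages through Cycle 1 and a jump at Cycle 3 Day 1. Every cohort would then show a decline as patients stop. A reader could take the first pattern for delayed onset and the second for tolerance. Characterising safety as monotherapy and in combination is a secondary objective (SAP 2.1.2), so the timing picture should reflect the drugs and not the calendar.

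**Working it through.** The documents give no figure for this table, so there is nothing to reproduce. The interval lengths come from the schedule; the event rates and retention below are assumptions shown over a range.

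**Step 1: interval lengths (nominal days, ignoring visit windows).**

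| Row | Cohort 1 | Cohorts 2 and 3 |
|---|---|---|
| Cycle 1 Day 7 | no visit | Day 1 to 7: 6 days |
| Cycle 1 Day 14 | no visit | Day 7 to 14: 7 days |
| Cycle 2 Day 1 (Day 22) | Day 1 to 22: 21 days | Day 14 to 22: 8 days |
| Later dosing visits | 21 days | 21 days |
| End of Treatment | up to 28 days | up to 28 days |

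The short intervals add up to one cycle: 6 + 7 + 8 = 21. This step needs no assumption about event rates.

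**Step 2: effect of interval length.** Let p be the probability of at least one event in 21 days, with constant hazard h = -ln(1 - p)/21. The probability in d days is 1 - exp(-h × d), among patients still observed.

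| d (days) | p = 30% | p = 50% | p = 70% |
|---|---|---|---|
| 6 | 9.7% | 18.0% | 29.1% |
| 7 | 11.2% | 20.6% | 33.1% |
| 8 | 12.7% | 23.2% | 36.8% |
| 21 | 30.0% | 50.0% | 70.0% |
| 28 | 37.8% | 60.3% | 79.9% |

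The Cycle 2 Day 1 row (21 days against 8) therefore reads 30% against 12.7%, 50% against 23.2%, or 70% against 36.8%, with the same risk in all cohorts.

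**Step 3: effect of the default denominator.** Let s be the share of patients retained from one cycle to the next, and suppose that patients off treatment add no events to later dosing-visit rows. With all treated patients as denominator, the k-th 21-day interval shows s^(k-1) × p. For p = 50% and k = 5:
- s = 70%: 0.70^4 × 0.5 = 12.0%
- s = 80%: 0.80^4 × 0.5 = 20.5%
- s = 90%: 0.90^4 × 0.5 = 32.8%

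The risk per patient on drug is 50% throughout.

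**Step 4: after the fix.** Under the same assumptions, equal 21-day intervals with patients on treatment as denominator read a flat 30%, 50% or 70% in every cycle and cohort.

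**Unassigned time.** The SAP's TEAE window runs to 70 days after varlilumab or the PD-1 inhibitor, so events after End of Treatment have no evident row. The row counted from first dose has no clear interval either, because SAP 5 defines baseline as on or before the day of first dose. Protocol Table 1 also marks adverse event monitoring at disease assessment visits, and SAP 9.2.1 does not say whether these count as a previous visit.

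**The case against.** The strongest case on the other side has four parts.

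- **The denominator is inferred.** The Protocol 11.5.3 sentence follows a description of summaries by system organ class and preferred term, and the protocol has no by-visit event table. An analysis population need not be the denominator at each visit: the ECOG summary in SAP 9.6 uses the same safety population but counts subjects at each planned assessment. This stands in part. A reader might infer that the SAP fixes all treated patients as the denominator for this table. It does not; that is only the default, which nothing in 9.2.1 overrides. Step 3 is conditional on it.
- **The cohorts do not differ throughout.** A reader might infer that every row is non-comparable across cohorts. The schedule does not support that: after Cycle 2 Day 1, dosing visits are 21 days apart in all three cohorts. The schedule artefact is confined to Cycle 1, the Cycle 2 Day 1 row and the post-treatment period. This stands.
- **No conclusion rests on the table.** It is descriptive, the cohorts are non-randomised and analysed separately, and the only cross-cohort comparison (Protocol 11.5.1) is exploratory and on efficacy. TEAE tables by class, term and grade, and the SAE tables, cover the whole TEAE period. Exposure, disposition and subject listings are also planned. This stands and sets the priority.
- **Day 7 and Day 14 detail is worth keeping.** Pooling these visits away would lose early-onset information on the combinations. This stands, and the fix keeps them.

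None of this removes the unequal intervals, which follow from the stated counting rule and the schedule.

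**Conclusion.** The point holds, at minor priority. Followed as written, SAP 9.2.1 gives a Cycle 2 Day 1 row that covers about 21 days in Cohort 1 and about 8 days in Cohorts 2 and 3. At equal risk the second figure is roughly half the first or less over the assumed range. Under the default denominator, later rows also shrink with attrition; if the table were instead built on patients attending each visit, that second effect would largely go and the first would remain.

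The sizes rest on a constant hazard and on assumed event rates and retention, none of which the documents give. The stronger conclusion that the trial's safety assessment is compromised is not supported: the effect is limited to this one table's picture of event timing, and no between-cohort test of adverse events is planned.

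**What to change.** Reword the last two sentences of SAP 9.2.1 so that the table is by treatment cycle in all cohorts.

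- **Intervals.** Run each cycle from its Day 1 to the day before the next cycle's Day 1, nominally 21 days. Add one post-last-dose interval to the end of the TEAE window, with its length printed by cohort. State where the last cycle closes, so that the two do not overlap. This also replaces the unclear baseline row and gives events after End of Treatment a place.
- **Denominator.** Use patients on treatment at the start of each cycle, and patients entering follow-up for the post-treatment interval. Print n in every row.
- **Early detail.** Keep Day 7 and Day 14 as sub-rows of Cycle 1 for Cohorts 2 and 3, labelled with their interval lengths.
- **Optional.** Add an exposure-adjusted rate. Under the Step 2 assumptions it is constant at 1.70, 3.30 or 5.73 per 100 patient-days, from 100 × h.

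The cost is a change of SAP wording and one re-programmed table. No new data are needed.
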